#### **7.5 Medical History and Concurrent Medical Conditions**

Medical history and concurrent medical conditions will be coded using the Medical Dictionary for Drug Regulatory Activities (MedDRA, Version 17.0 or later) coding system.

Frequencies and percentages of subjects by medical history and concurrent medical conditions will be summarized by system organ class (SOC) and preferred term (PT) for the safety population and by age group, dose group and formulation arm. Multiple entries for an individual patient under the same SOC/PT will only be counted once

#### **7.6 Medication History and Concomitant Medications**

Medication history and concomitant medications will be coded using the World Health Organization DRUG dictionary (WHODrug, 01MAR2014 version or later).

Medication history includes all medication that was taken but ended at informed consent or within 3 months prior to the time of informed consent. Concomitant medications include medications taken from informed consent through post-study follow-up.

Frequencies and percentages of subjects by medication history and concomitant medications will be summarized by preferred medication name for the safety population and by group, dose group and formulation arm. Subjects with multiple uses of a medication history or concomitant medication will be counted once for a given preferred medication name.

A glossary of medication history and concurrent medications by preferred medication name will be presented.

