### 7.2 Exclusion Criteria

Any subject who meets any of the following criteria will not qualify for entry into the trial:

1. Subjects with a clinically significant active infection (as assessed by the investigator) or body temperature 38.0°C (100.4°F) or higher within 3 days of the intended date of vaccination.
2. Subjects who have received antipyretic/analgesic medications within 24 hours prior to the intended vaccine administration.
3. Known hypersensitivity or allergy to investigational vaccine (including excipients of the investigational vaccines as summarized in protocol Section [8.1](#)).
4. Subjects with behavioral or cognitive impairment or psychiatric disease that, in the opinion of the investigator, may interfere with the subject's ability to participate in the trial.
5. Subjects with a history of any progressive or severe neurologic disorder, seizure disorder, or neuroinflammatory disease (eg, Guillain-Barré syndrome).
6. Known or suspected impairment/alteration of immune function, including the following:
  - a. Children <18 months of age with history of repeated episodes of acute otitis media (AOM) [\[32\]](#) in the first 6 months of life (AOM defined as a bulging tympanic membrane) and not to be confused with otitis media with effusion (OME).

- b. Chronic use of oral steroids (equivalent to 20 mg/day prednisone for  $\geq 12$  weeks/ $\geq 2$  mg/kg body weight/day for  $\geq 2$  weeks) within 60 days prior to Day 1 (use of inhaled, intranasal, or topical corticosteroids is allowed).
- c. Receipt of parenteral steroids (equivalent to 20 mg/day prednisone  $\geq 12$  weeks/ $\geq 2$  mg/kg body weight/day for  $\geq 2$  weeks) within 60 days prior to Day 1.
- d. Receipt of immunostimulants within 60 days prior to Day 1.
- e. Receipt of parenteral, epidural, or intra-articular immunoglobulin preparation, blood products, and/or plasma derivatives within 3 months prior to Day 1 or planned during the full length of the trial.
- f. Receipt of immunosuppressive therapy within 6 months prior to Day 1.
- g. Human immunodeficiency virus (HIV) infection or HIV-related disease.
- h. Chronic Hepatitis B or C infection.
- i. Heritable immunodeficiency.

- 7. Abnormalities of splenic or thymic function.
- 8. Subjects with a known bleeding diathesis or any condition that may be associated with a prolonged bleeding time.

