### **7.3 Criteria for Delay of Vaccination and Blood Sampling**

After enrollment, subjects may encounter clinical circumstances that warrant a delay in subsequent trial vaccination. These situations are listed below:

- Subjects with a body temperature 38.0°C (100.4°F) or higher within 3 days of intended trial vaccination.
- Subjects who have received antipyretics/analgesic medications within 24 hours prior to the intended vaccine administration.
- Subjects who have received blood, blood products, and/or plasma derivatives or any parenteral immunoglobulin preparation in the past 3 months (prior to initial vaccination).

If the subject cannot be randomized and vaccinated on Day 1 due to a temporary contraindication and must return at a later time, the same identification number (screening number) should be kept. If the subject randomization visit is re-scheduled for more than 15 days after the screening, then a new ICF should be obtained.

For subsequent vaccination visits, it is strongly recommended to schedule them as early in the visit window as possible, in case these visits need to be re-scheduled due to a vaccination and/or blood sampling temporary contraindication.

There are also circumstances under which receipt of further vaccines is a contraindication in this trial. These circumstances include anaphylaxis or severe hypersensitivity reactions following the initial vaccination. If these reactions occur, the subject must not receive additional vaccinations, but is encouraged to continue in trial participation for safety reasons.

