#### 9.1.2 Demographics, Medical History and Medication History Procedure

Demographic information to be obtained will include age, sex, race as described by the subject or subject's legal guardian.

Medical history will also be collected, including but not limited to any medical history that may be relevant to subject eligibility for trial participation such as prior vaccinations, concomitant medications, and previous and ongoing illnesses or injuries. Relevant medical history can also include any medical history that contributes to the understanding of an AE that occurs during trial participation, if it represents an exacerbation of an underlying disease/pre-existing problem.

Adverse medical occurrences that occur after the ICF and assent form (where applicable) have been signed, but before administration of the vaccine, will be documented in the Medical History eCRF.

All prescription medications, vaccines and blood products taken or received by the subjects within 3 months prior to the start of the trial are to be recorded on the Prior and Concomitant Medications eCRF. The use of antipyretics and/or analgesic medications within 24 hours prior to vaccination must be identified and the reason for their use (prophylaxis versus treatment) must be described in the source documents or the eCRF. Trial vaccination should be delayed if subjects have used antipyretics/analgesic medications within 24 hours prior to vaccine administration.

Medications taken for prophylaxis are those intended to prevent the onset of AEs following vaccination. Medications taken for treatment are intended to reduce or eliminate the presence of symptoms that are present.

Assess and record concomitant therapy (prescription medications ONLY) and vaccine history from 3 months prior to Day 1 in the subject's source document.

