### **9.3.3 Post-vaccination Procedures (Day 1 and Day 29 [Cohort 1] and Day 1, Day 56, and Day 112 [Cohort 2])**

The following post-vaccination procedures will be performed on Day 1 and Day 29 (Cohort 1), and Day 1, Day 56, and Day 112 (Cohort 2).

- Careful training of the subject's LAR on how to measure local AEs and body temperature, how to complete the diary card, and how often to complete the diary card. Training should be directed at the individual(s) who will perform the measurements of local AEs and those who will enter the information into the diary card. This individual may or may not be the subject's LAR, but if a person other than the subject's LAR enters information into the diary card, this person's identity must be documented in the trial file and this person must receive training on the diary card. Training of the subject's LAR on how to measure an injection site reaction should be performed while the subject is under observation after vaccination.

Diary card instructions must include the following:

- The subject's LAR must understand that timely completion of the diary card on a daily basis is a critical component of trial participation. The subject's LAR should also be instructed to write clearly and to complete the diary card in pen. Any corrections to the diary card that are

performed by the person completing the diary card should include a single strikethrough line with a brief explanation for any change and be initialed and dated.

Please note:

Diary cards will be the only source document allowed for remote collection of solicited local and systemic AEs (including body temperature measurements). The following additional rules apply to the documentation of safety information collected by diary card:

- The Diary Card should be reviewed with the subject's LAR.
- No corrections or additions to the diary card will be allowed after it is reviewed with the investigator/designee.
- Any data that is identified as implausible or incorrect, and confirmed by the subject's LAR to be a transcription error should be corrected by the subject's LAR on the diary card (the correction should include a single strikethrough line and should be initialed and dated by the subject's LAR).
- Any blank or illegible fields on the diary card not otherwise corrected as above will be missing in the eCRF.
- The site must enter all readable entries on the diary card into the eCRF.

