- Any newly described solicited safety information should be added to the diary card by the subject's LAR or by the person who is authorized by the subject's LAR to complete the diary, then initialed and dated. Any new unsolicited safety information such as a verbally reported event, should also be recorded in the subject medical chart (as recorded on the diary card/source document) and captured as an AE and recorded in the AE eCRF.
- Starting on the day of vaccination, the subject's LAR will check for specific types of events at the injection site (solicited local AEs), any specific generalized symptoms (solicited systemic AEs), body temperature (any method), any other symptoms or change in the subject's health status, and any medications taken (excluding vitamins and minerals). These solicited AEs and body temperature will be recorded in the diary. Assessments should preferably take place in the evening at day's end.
- Temperature measurement is to be performed using the thermometer provided by the site. If the subject feels unusually hot or cold during the day, the subject's LAR should check their temperature. If the subject has fever, the highest body temperature observed that day should be recorded on the diary card.
- The measurement of solicited local AEs (erythema, swelling, and induration) is to be performed using the ruler provided by the site.
- The collection on the diary card of body temperature, solicited local AEs, and solicited systemic AEs will continue for a total of 7 days following vaccine administration. The collection on the diary card of unsolicited AEs and medications will continue for 28 days following vaccine administration.

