#### Subjects’ Legal Guardian Assessments of Reactogenicity via Subject’s Diary

Reactogenicity is also assessed by the subject’s legal guardian for 7 days following each vaccination (day of vaccination and the following 6 days) via diary collection of solicited AEs. These include local events (injection site pain, erythema/redness, induration, and swelling) and systemic events of headache, fatigue, myalgia, arthralgia, vomiting (number per day/intensity), and diarrhea (number per day/consistency) for children aged 4 to <9 years; and irritability/fussiness, drowsiness, loss of appetite, vomiting (number per day/intensity), and diarrhea (number per day/consistency) for children aged 6 weeks to < 4 years. Measurements of the largest diameter for injection site erythema/redness, swelling, and induration are collected. These measurements will be used to derive severity grades based on the criteria presented in [Appendix A](#) and [Appendix B](#). Temperature measurements are also collected and a systemic event of ‘fever’ will be derived as Yes/No based on temperature  $\geq$  38 degrees centigrade. Temperature levels will also be categorized in 0.5 degree intervals (centigrade). Severity categories for each solicited AE are defined in Protocol Section 9.1.7. In addition, the relationship of solicited systemic symptoms occurring within 7 days after each vaccination is assessed by the investigator during diary review.

For each solicited AE, the percentage of subjects will be summarized by event severity for each day for the 7 days following vaccination (including the day of vaccination) and overall within the 7 days following vaccination. In addition, summaries will be provided for the intervals of Days 1 to 3 and Days 4 to 7 following each vaccination. For subjects with more than 1 episode of the

same event within an interval (overall within the 7 days following vaccination, days 1-3, and days 4-7), the maximum severity will be used for tabulations.

The relationship of solicited systemic symptoms occurring within 7 days after each vaccination will also be tabulated. If a subject reported more than one episode of the same event, then the strongest relationship will be included in the summaries.

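### Antipyretic use after each injection is recorded but not tabulated by injection or 7-day window, so attenuated fever differences between arms would not be visible

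*SAP*

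**What the plan says.** Before an injection, the protocol takes these medicines seriously. Exclusion criterion 2 in Protocol 7.2 covers "Subjects who have received antipyretic/analgesic medications within 24 hours prior to the intended vaccine administration", and Protocol 7.3 makes the same circumstance a reason to delay later injections. Protocol 9.1.2 adds: "The use of antipyretics and/or analgesic medications within 24 hours prior to vaccination must be identified", with the reason recorded as preventive or as treatment.

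After an injection, use is recorded. Under Protocol 9.3.3 the caregiver notes symptoms, temperature "and any medications taken (excluding vitamins and minerals"), and medication entries continue for 28 days after each dose. The same section states: "The site must enter all readable entries on the diary card into the eCRF".

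In the analysis, SAP 7.6 defines concomitant medication as anything from consent through follow-up. These data "will be summarized by preferred medication name for the safety population and by group, dose group and formulation arm", and repeated use of the same product counts once per child. SAP 7.11.1, on the diary data, begins "Temperature measurements are also collected and a systemic event of" and goes on to derive fever as yes or no at 38 °C. It summarises solicited events by diary day and for Days 1-7, 1-3 and 4-7 after each injection. It does not mention medication.

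**The concern.** Solicited reactions and body temperature are primary safety endpoints, and the primary objective is to select a formulation partly on them. Fever depends on a threshold, so a child given an antipyretic before reaching 38 °C is counted as having no fever. Use after the injection can respond to how the child is doing, so randomisation and blinding do not guarantee that it is balanced between arms. If it is more common or earlier where reactions are worse, the observed fever rate falls most in the arm with the highest underlying rate.

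The SAP 7.6 table is not built to show this. A dose of paracetamol on the evening of the first injection and one given weeks later for a cold fall into the same cell. A child who uses two products appears in two rows, so use of the class cannot be recovered by adding rows. Neither the injection number nor the 7-day window appears.

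**Working it through.** **Plan's own figure.** The only sample-size calculation is Protocol Table 13-a. It reproduces: for example, 1 − (1 − 0.0033)^480 = 79.5%. It concerns seeing at least one event and says nothing about differences between arms, so this point does not depend on it.

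**Time units side by side.**
- Fever (SAP 7.11.1): each injection, each diary day, Days 1-7, 1-3 and 4-7, by arm.
- Medication (SAP 7.6): one window for the whole of participation, by product name, by arm.

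The two tables share the arm but not the injection or the interval, so they cannot be read together.

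**Size, by illustration.** The documents give no fever rate, usage rate or drug effect. All inputs below are assumed.
- p: fever rate without medication, 20% in the higher arm and 10% in the lower.
- u: share of would-be febrile children given an antipyretic in the window.
- e: share of those kept below 38 °C.
- Observed rate = p × (1 − u × e).

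| Assumption | Higher arm | Lower arm | Difference |
|---|---|---|---|
| No medication effect | 20.0% | 10.0% | 10.0 points |
| u × e = 0.15 in both arms | 0.20 × 0.85 = 17.0% | 0.10 × 0.85 = 8.5% | 8.5 points |
| u × e = 0.30 in both arms | 0.20 × 0.70 = 14.0% | 0.10 × 0.70 = 7.0% | 7.0 points |
| u = 60% vs 20%, e = 30% | 0.20 × 0.82 = 16.4% | 0.10 × 0.94 = 9.4% | 7.0 points |
| u = 60% vs 20%, e = 50% | 0.20 × 0.70 = 14.0% | 0.10 × 0.90 = 9.0% | 5.0 points |
| u = 60% vs 20%, e = 70% | 0.20 × 0.58 = 11.6% | 0.10 × 0.86 = 8.6% | 3.0 points |

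The equal-suppression rows need only that some fevers are prevented. The last three rows also need would-be febrile children to be medicated more often in one arm than in the other. That could happen if other symptoms prompt earlier dosing there, but the documents neither show it nor rule it out.

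**Boundary.** With e = 70% and no use in the lower arm, the 10-point difference disappears only when u in the higher arm reaches (1 − 0.10/0.20)/0.70 = 71%. Across the tabulated range the difference shrinks but does not vanish.

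**Can the existing data show it?** Protocol 9.3.3 puts the medication entries on the diary card and readable entries into the eCRF. SAP 7.1 already derives day relative to each dose, and the diary intervals are already defined. Recorded antipyretic use can therefore be placed in the same windows as fever.

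**The case against.** Much of the case on the other side is sound.

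- **The route to masking is narrow.** Caregivers are told to take the temperature if the child seems hot or cold, and to write down the day's peak when there is fever. A fever measured before treatment still counts. Temperature is also shown in 0.5-degree bands. What remains is preventive use, or treatment before 38 °C has been measured.
- **SAP 7.6 is not empty.** It is split by arm. Medication follow-up runs mainly for 28 days after each dose, and the later safety calls take only medicines linked to SAEs. A gross imbalance in one named product would show. It would still not show by injection, in the 7-day window or for the class. Subject listings would hold the detail, but they are not summaries, and SAP 7.12 provides complete listings only at the final analysis.
- **The design is descriptive.** The listed pairwise comparisons concern immunogenicity. With about 15 children per arm and group, 10 points is 1.5 children; with about 45 per arm in Cohort 2 it is 4.5. Reporting reactions under actual medication use is a legitimate target. Reading it properly still requires knowing what that use was.

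A reader might also infer that pain grades are masked in the same way. For ages 4 to under 9 the documents do not support that: Protocol Table 9-a applies pain grades 2 and 3 whether or not the child was treated, and SAP 7.11.1 tabulates maximum severity. Table 9-b, for younger children, has no such wording for pain, so a usage table gives context there, but no size is claimed.

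**Conclusion.** The gap is real and modest. Post-injection antipyretic and analgesic use is collected, yet no planned summary relates it to the injection or to the 7-day window in which fever is assessed. A fever difference between formulations could be attenuated without the tables revealing it. Under the assumed 20% versus 10%, the loss is 1.5 to 3 points with equal suppression of 15% to 30%, and 3 to 7 points with 60% versus 20% use and 30% to 70% suppression. These figures show a possibility; they are not estimates for this trial.

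Three stronger conclusions do not follow:
- **Near-disappearance of the difference.** Shrinking 10 points to 2 would need, for example, 50% suppression in one arm against 20% in the other. Families are blinded to formulation, and no document supports such a split.
- **Bias in a vaccine-versus-saline contrast.** No such reactogenicity comparison is specified; the saline injection is there to keep the blind.
- **A need to control medication after injection.** This is a point about tabulation, and nothing here says what families should or should not give.

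The point is therefore a cheap improvement to the safety tables. It does not show that the planned fever analysis is invalid.

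**What to change.** Add two summaries to SAP 7.11.1, both from existing diary entries:

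1. Number and percentage of children with any antipyretic or analgesic, as a class, on Days 1-7, 1-3 and 4-7 after each injection, by group and formulation/dose arm.
2. Number and percentage with temperature of 38 °C or more or antipyretic use on the same days, shown beside the fever table as a supplement and not in place of it.

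Also reconcile two protocol statements. The concomitant-therapy instruction in 9.1.2, covering the period from 3 months before Day 1, is limited to prescription products; the diary in 9.3.3 takes any medicine except vitamins and minerals. It should be clear that non-prescription antipyretics recorded in the diary reach the database.

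The cost is two tables and a list of the products that make up the class. The downside is that the composite also counts antipyretics given for unrelated illness, which is why it only supplements the fever table. A new field for the reason for post-injection use is not recommended: Groups 1 and 2 have already been vaccinated, and it would require new data collection.

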## **7.7 Duration of Follow up and Vaccine Regimen Compliance**

Compliance rate will be summarized by the 8 formulation/dose combinations for each group, by presenting the number and percentage of subjects receiving each vaccine dose. The vaccination date/time information will be listed for each subject. The duration of follow-up will be summarized as a continuous variable, and also as a frequency and percentage of subjects in the following categories: (1.1) 1 – 29 days, (1.2) 30 - 57 days, (1.3) > 57 days for cohort 1 and (2.1) 1 - 56 days, (2.2) 57 - 112 days, (2.3) 113 - 140 days, (2.4) >140 days for cohort 2. The duration of follow-up is defined as the number of days from the first vaccination to the date of last contact specified on the End of Study Visits form. This will generally be the date of the last clinic visit but could be a phone contact. For interim analyses, if the End of Study Visits form is not available, the date of data cutoff will be used for calculation

## **7.8 Immunogenicity Analysis**

### *General Methodology*

The primary population for immunogenicity analyses will be the PPS. Supportive immunogenicity analyses on primary and key secondary endpoints will also be performed using FAS.

Descriptive statistics for the primary, secondary, and exploratory endpoints will be computed for all available assays at all relevant time points and include the following:

- Titer values (eg, GMT, BT50, GMFR): geometric mean, GSD, 95% CIs, minimum, and maximum;
- Other continuous endpoints: mean, SD, median, minimum, and maximum;
- Categorical variable (eg, seroresponse rate): number and percentage of subjects, and 95% CIs in specified categories. The 95% CI of seroresponse rate will be calculated using exact (Clopper-Pearson) method.

Cohorts will be analyzed separately due to different number of doses (1 or 2 in Cohort 1; 2 or 3 in Cohort 2).

Analysis of covariance (ANCOVA) will be conducted for continuous outcome parameters (eg, GMT, GMFR), examining the effect of formulation/dose combination using log-transformed values of the endpoint as the dependent variable and the corresponding log-transformed baseline (pre-vaccination) value as a continuous covariate. The ANCOVA models will include group as a factor for analyses of Cohort 1 with a group by formulation/dose combination interaction term if

appropriate as follows. If the interaction term p-value is  $\leq 0.05$ , the term will remain in the model. If the p-value is  $>0.05$  it will be removed. For Cohort 1, the model will include estimates for treatment (formulation/dose combination) effect within each group, and at the cohort level across groups. A factor for country will be included in all models.

For binomial outcomes the Cochran-Mantel-Haenszel (CMH) method [2] for difference in proportions will be conducted, stratified by group (Cohort 1).

All pairwise comparisons (with the lower level as a reference group) will be presented, without adjustments for multiplicity.

Pre-specified comparisons of interest will be tested. The pre-specified comparisons of interest are the following:

- “A: 15/15, 1 Dose” vs. “A: 15/15, 2 Dose”
- “A: 15/15, 1 Dose” vs. “B: 15/50, 2 Dose”
- “B: 15/50, 1 Dose” vs. “C: 50/50, 1 Dose”
- “B: 15/50, 1 Dose” vs. “B: 15/50, 2 Dose”
- “C: 50/50, 1 Dose” vs. “B: 15/50, 2 Dose”
- “C: 50/50, 1 Dose” vs. “C: 50/50, 2 Dose”
- “C: 50/50, 1 Dose” vs. “D: 50/150, 2 Dose”
- “D: 50/150, 1 Dose” vs. “D: 50/150, 2 Dose”
- “A: 15/15, 2 Dose” vs. “B: 15/50, 2 Dose”
- “A: 15/15, 2 Dose” vs. “C: 50/50, 2 Dose”
- “A: 15/15, 2 Dose” vs. “D: 50/150, 2 Dose”
- “B: 15/50, 2 Dose” vs. “C: 50/50, 2 Dose”
- “B: 15/50, 2 Dose” vs. “D: 50/150, 2 Dose”
- “C: 50/50, 2 Dose” vs. “D: 50/150, 2 Dose”.

Subjects with baseline values below the LLoQ for all assays (Pan-Ig, HGBA, and IgA) and VLP antigens (GI.1 and GII.4) will be identified. If warranted, selected immunogenicity summaries may be prepared for subsets of interest.

